4.1.5 Blinding and procedures for unblinding

4.1.5.1 Blinding

This is an open-label trial; treatment allocation to the Investigators and patients will not be concealed throughout the study. The eCRF will contain information on randomised treatment. Trial medication will be identified by a medication code number. Despite the trial being open label, all activities conducted by the trial team will be performed in a blinded manner until database lock.

For justification of the PROBE design chosen for this study see [Section 3.2](#).

4.1.5.2 Procedures for emergency unblinding

Not applicable.

4.1.6 Packaging, labelling, and re-supply

Dabigatran etexilate will be provided in kits. Each kit will contain four bottles that each contains 60 capsules of either 110mg or 150mg dabigatran etexilate. The number of kits provided to the patient will vary depending on the time between visits.

Patients on warfarin will receive the required combination of 1mg, 3mg and 5mg tablets in bottles or blister packs according to their actual needs as defined by the measured INR value. Each warfarin bottle will contain 66 tablets. Each blister pack will contain 70 tablets. Warfarin supplies should be checked at each visit to ensure the patient has sufficient quantity and that expiry dates will not be compromised prior to the next clinic visit.

Supply and re-supply will be managed by the IRT.

For details of packaging and the description of the label, refer to the ISF.

4.1.7 Storage conditions

Patients should be instructed to keep medication containers tightly closed and not to remove tablets/capsules from original package material until immediately prior to time of intake. It is not allowed to use medication from more than one dabigatran etexilate kit at the same time.

Proprietary confidential information.

© 2016 Boehringer Ingelheim International GmbH or one or more of its affiliated companies. All rights reserved.

This document may not - in full or in part - be passed on, reproduced, published or otherwise used without prior written permission.

Trial medication must be stored under the recommended storage conditions indicated on the label. A temperature log must be maintained by the Investigator / pharmacist / investigational drug storage manager to make certain that the drug supplies are stored at the correct temperature. If the storage conditions are found to be outside the specified range, the process outlined in the ISF should be followed.

Trial medication must be stored securely at the study sites, out of reach of children and be protected from moisture and direct sunlight, e.g. in a locked cupboard or at a pharmacy. It may only be dispensed to trial patients fulfilling the inclusion and exclusion criteria by authorised study personnel as documented in the ISF. Receipt, usage and return of the study medication must also be documented on the respective forms in the ISF.

All unused medication including bottles, blisters and outer boxes (empty or filled) must be either returned to the Sponsor, or, following written authorisation from the Sponsor, may be destroyed at site. Receipt, usage and return must be documented on the respective forms. Account must be given for any discrepancies.

4.1.8 Drug accountability

The Investigator, pharmacist/investigational drug storage manager will receive the investigational drugs delivered by the sponsor when the following requirements are fulfilled:

- approval of the study protocol by the IRB / IEC,
- availability of a signed and dated clinical trial contract between the sponsor and the Head of Trial Centre,
- approval/notification of the regulatory authority, e.g. competent authority,
- availability of the curriculum vitae of the Principal Investigator,
- availability of a signed and dated CTP or immediately imminent signing of the CTP (in exceptional cases, medication could already be sent to the site, before its activation via IRT)
- availability of the proof of a medical licence for the Principal Investigator, if applicable
- For USA, availability of the Form 1572.

The Investigator, pharmacist/ investigational drug storage manager must maintain records of the product's delivery to the trial site, the inventory at the site, the use by each patient and the return to the sponsor or alternative disposition of unused product(s).

These records will include dates, quantities, batch/serial numbers, expiry ('use by') dates and the unique code numbers assigned to the investigational product(s) and trial patients. The Investigator / pharmacist / investigational drug storage manager will maintain records that document adequately that the patients were provided the doses specified by the CTP and reconcile all investigational product(s) received from the sponsor.

At the time of return to the sponsor, the Investigator / pharmacist / investigational drug storage manager must verify that all unused or partially used drug supplies have been returned by the clinical trial patient and that no remaining supplies are in the Investigator's possession.

Proprietary confidential information.

© 2016 Boehringer Ingelheim International GmbH or one or more of its affiliated companies. All rights reserved.

This document may not - in full or in part - be passed on, reproduced, published or otherwise used without prior written permission.

For non-investigational medicinal products (NIMPs), a system allowing traceability will be implemented (please refer to [Section 4.2.1](#) for the definition of a NIMP in this trial). This will include the following:

- documentation of intake of the NIMP in the source data (e.g. name of NIMP, how much and when it was taken [but no unit count will be necessary])
- documentation of intake of NIMP in the eCRF.

4.2 CONCOMITANT THERAPY, RESTRICTIONS, AND RESCUE TREATMENT

Any additional drugs considered necessary for the patient's welfare may be given at the discretion of the Investigator and with due consideration of the information provided below.

Comprehensive details of concomitant medication of special interest (e.g. antiplatelet medication, parenteral anticoagulant, thrombolytic agent, GPIIb/IIIa antagonist, VKA, therapies for bleeding management, novel direct oral anticoagulant) administered to the patient from 30 days prior to Informed Consent until the patient completes follow-up should be recorded in the eCRF. Abbreviated information will be collected for any other concomitant therapy.

Certain concomitant therapies (e.g. fibrinolytics, anticoagulants other than warfarin/dabigatran etexilate) or surgery/intervention may require the temporary discontinuation of warfarin or dabigatran etexilate. Study medication should be restarted as soon as safely possible. In case of a temporary interruption, bridging therapy with a parenteral anticoagulant is allowed at the discretion of the Investigator (see [Appendix 10.1](#) for guidance on bridging therapy). Following study drug discontinuation due to AEs (e.g. bleeds) the patient should be treated according to local clinical practice. After resolution of an AE, consideration should be given to resuming study medication at the assigned dose.

The concomitant administration of PPIs is strongly recommended in patients without clinical contraindications for those agents, to reduce the risk of GI bleeding. In patients receiving clopidogrel, PPIs that do not interact with the CYP2C19 (lansoprazole, pantoprazole, etc.) should be used.

4.2.1 Rescue medication, emergency procedures, and additional treatments

In this trial clopidogrel, ticagrelor and ASA are considered a NIMP. This means that in the event of a serious adverse event (SAE), the Investigator will assess the causal relationship of the SAE to the NIMP. Further details regarding SAE reporting can be found in [Section 5.2.2.3](#).

The Investigator is responsible for ensuring that procedures and expertise are available to cope with medical emergencies that may occur during the study.

Proprietary confidential information.

© 2016 Boehringer Ingelheim International GmbH or one or more of its affiliated companies. All rights reserved.

This document may not - in full or in part - be passed on, reproduced, published or otherwise used without prior written permission.

4.2.1.1 Major Bleeds

Dabigatran Etexilate Treated Group:

If a patient experiences major bleeding, the study medication should be temporarily stopped and the source of bleeding investigated and treated. This will generally involve coagulation testing (e.g. aPTT, TT, ECT), platelet count, and possibly transfusion, diagnostic procedures and/or surgical haemostasis.

The recommendations given below are derived from guidelines to manage bleeding with dabigatran etexilate. See [Section 4.2.1.7](#) Overdose, for more information regarding the specific reversal agent for dabigatran.

Since dabigatran is excreted predominantly by the renal route adequate diuresis must be maintained. Appropriate standard treatment, e.g. surgical haemostasis as indicated and volume replacement should be undertaken as appropriate. In addition, consideration may be given to the use of fresh frozen plasma [[P10-03790](#), [P13-06400](#)]. As protein binding is low, dabigatran is dialysable, however there is limited clinical experience in using dialysis in this setting. Clearance of dabigatran by haemodialysis was investigated in patients with end-stage renal disease. Dialysis was conducted with 700mL/min dialysate flow rate, four hour duration, a blood flow rate of either 200mL/min or 350 - 390mL/min. This resulted in a removal of 50% or 60% of free or total dabigatran concentrations, respectively. The amount of drug cleared by dialysis is proportional to the blood flow rate. There is some experimental evidence to support the role of agents such as activated prothrombin complex concentrates (APCC, e.g. FEIBA), recombinant Factor VIIa and three- or four-factor concentrates (Factors II, IX and X with or without Factor VII) in reversing the anticoagulant activity of dabigatran. The usefulness in clinical settings has not yet been systematically demonstrated. Consideration should also be given to administration of platelet concentrates in cases where thrombocytopenia is present or long acting antiplatelet drugs have been used. All symptomatic treatment will be given according to the treating physician's judgement.

Re-administration of study medication (at the same dose as before) after the bleeding has resolved and haemostasis has been achieved, is at the discretion of the Investigator. In the case of a temporary stop of dabigatran etexilate bridging therapy with a parenteral anticoagulant with e.g. UFH or LMWH (according to local practice) is at the discretion of the Investigator. See [Appendix 10.1](#) for additional information related to bridging.

A summary of how to manage bleedings on dabigatran etexilate is presented in [Figure 4.2.1.1: 1](#).

Proprietary confidential information.

© 2016 Boehringer Ingelheim International GmbH or one or more of its affiliated companies. All rights reserved.

This document may not - in full or in part - be passed on, reproduced, published or otherwise used without prior written permission.

[figure not shown]

Figure 4.2.1.1: 1 Management of bleeding on dabigatran therapy [[P10-03790](#)]

Warfarin Treated Group:

If a patient experiences a major bleed warfarin should be temporarily stopped. The anticoagulant effect of VKAs can be reversed with vitamin K, prothrombin complex concentrates and/or fresh frozen plasma. Re-administration of warfarin after the bleeding has resolved and haemostasis has been achieved is at the discretion of the Investigator. Bridging therapy, e.g. UFH until the INR has returned back to the target range, is at the discretion of the Investigator (see [Appendix 10.1](#)).

4.2.1.2 Minor Bleeds

If a patient experiences a minor bleed, study medication may be continued, interrupted temporarily or permanently discontinued, at the discretion of the Investigator. It is not a requirement, however, that study drug be stopped in these cases.

Proprietary confidential information.

© 2016 Boehringer Ingelheim International GmbH or one or more of its affiliated companies. All rights reserved.

This document may not - in full or in part - be passed on, reproduced, published or otherwise used without prior written permission.

4.2.1.3 Emergency and Elective Surgery

Dabigatran Etexilate Treated Group:

Preoperative Phase:

Emergency Surgery

In the case of emergency surgery, study medication should be discontinued. If possible, surgery should be postponed until 12 hours, or longer in case of renal failure, after the last oral intake of study drug.

In an emergency event, a measure of anticoagulation may become necessary to manage the situation. A physician may consider using the TT or diluted TT (where available), activated partial thromboplastin time (aPTT) or the ECT. For further details on results of coagulation times expected with dabigatran, see section on elective surgery below.

See [Section 4.2.1.7](#) Overdose, for more information regarding the specific reversal agent for dabigatran.

Elective Surgery

Physicians may consider the following information regarding dabigatran etexilate when patients need to undergo surgery or elective procedures. Providing the patient has normal renal function, the onset of effect of dabigatran is within 1 hour of dosing and dabigatran has peak concentrations 2-3 hours after an oral dose. Steady state is reached within 2-3 days. Plasma levels of dabigatran in steady state will vary across the population and are particularly affected by renal function. Patients with renal dysfunction may have elevated concentrations of dabigatran due to longer half-lives of active drug [see [Table 4.2.1.3: 1](#)]. Serum creatinine should normally be checked 1-2 weeks before surgery and the CrCl should be calculated using the Cockcroft-Gault formula ([Section 5.2.3](#)). Patients with a CrCl <30mL/min during the course of this study should not be receiving study medication (see [Section 3.3.4.1](#)).

The following is a guide to the discontinuation of dabigatran etexilate (under special consideration of the half-life of dabigatran depending on renal function) before surgery taking renal function and additional risk factors into account. In patients with normal renal function, discontinuation of two doses of dabigatran etexilate will decrease plasma levels to approximately 25% of steady state trough levels and discontinuation of four doses will decrease dabigatran plasma levels to approximately 5-10% of steady-state trough levels.

Proprietary confidential information.

© 2016 Boehringer Ingelheim International GmbH or one or more of its affiliated companies. All rights reserved.

This document may not - in full or in part - be passed on, reproduced, published or otherwise used without prior written permission.

Table 4.2.1.3: 1 Recommendations on cessation of study drug in relation to the timing of major surgery

Renal function (CrCl, mL/min) ¹	Estimated half- life if on dabigatran etexilate	Stop study dabigatran etexilate before surgery	
		High Risk of bleeding ²	Standard Risk
≥80	~ 13 hours	2 days before	24h prior (2 doses)
≥50 to <80	~ 15 (12-18) hours	2-3 days before	1-2 days before
≥30 to <50	~18 (18-24) hours	4 days before	At least 2 days (>48 hours)
<30	~ 27 (>24) hours	>5 days before	2-5 days

¹ CrCl can be estimated using serum creatinine by the Cockcroft-Gault formula (see [Section 5.2.3](#)). Patients who develop CrCl <30mL/min during the course of the trial should have study medication stopped (see [Section 3.3.4.1](#)).

² In addition to renal function, high risk determinants of bleeding risk include type of surgery, advancing age, comorbidities (e.g. major cardiac, respiratory or liver disease) and concomitant use of antiplatelet therapy. The type of surgery associated with a high risk of bleeding includes but is not limited to cardiac surgery, neurosurgery, abdominal surgery or those involving a major organ. Other procedures such as spinal anaesthesia may also require complete haemostatic function.

In patients at high risk of bleeding, including those in whom severe renal dysfunction may occur in the course of the trial (<30mL/min CrCl), an elevated thrombin clotting time (TT) or diluted thrombin time ((dTT); only in countries where this assay is approved) should lead the clinician to consider delaying surgery. If the TT/dTT test is not available, an aPTT, though less precise than the TT, can be used. A TT/dTT should be performed 6-12 hours before elective surgery and a normal result as defined by the local lab should be obtained before a patient undergoes surgery. A persistently prolonged thrombin time (TT or dTT) in the absence of heparin, fibrin/fibrinogen degradation products (e.g. with disseminated coagulation activation, sepsis, severe inflammation and other conditions) or high concentrations of serum proteins (e.g. myeloma) suggests persistently elevated levels of dabigatran in the blood.

In patients receiving chronic therapy with dabigatran etexilate 110mg b.i.d., the median peak aPTT is approximately 57 sec [[U09-3249-02](#)]. Assuming the baseline range of normal is between 22 to 40 sec (aPTT assay as used in RE-LY) this peak aPTT prolongation corresponds to approximately 2 times control [[U11-1855-01](#)]. Twelve hours after the last dose, the median aPTT is approx. 1.7 times control [[U09-3249-02](#)], (median trough aPTT prolongation for patients receiving 110mg BID in RE-LY: 48 sec) given adequate renal function, with less than 10% of patients exceeding 2.4 times control [[U11-1855-01](#),[U09-3249-02](#)], (90th percentile trough aPTT prolongation for patients receiving 110mg b.i.d. in RE-LY: 69 sec). ECT shows a close linear correlation with the plasma concentrations of direct thrombin inhibitors, including dabigatran. Median ECT ratios over baseline of approx.1.8 at trough and 2.5 [[U11-1855-01](#)] at peak, have been observed after intake of dabigatran etexilate 110mg b.i.d. Coagulation times should be interpreted in relation to the timing of last drug intake of study medication (peak versus trough dabigatran levels). The

Proprietary confidential information.

© 2016 Boehringer Ingelheim International GmbH or one or more of its affiliated companies. All rights reserved.

This document may not - in full or in part - be passed on, reproduced, published or otherwise used without prior written permission.

current version of the IB should be referenced for further information about dabigatran etexilate.

Post Procedural Period:

With the exception of cardiac surgery, dabigatran etexilate will be initiated as soon as the patient is haemodynamically stable and haemostasis is achieved. If oral medication is not feasible, bridging therapy with i.v. or subcutaneous (s.c.) UFH or s.c. Low Molecular Weight Heparin (LMWH) should be considered at the discretion of the Investigator (see [Appendix 10.1](#)).

Note: In patients where renal function is impaired or procedures undertaken which may temporarily compromise renal function, a serum creatinine should be performed and CrCl calculated based on the Cockcroft-Gault formula. In patients receiving dabigatran etexilate, if CrCl drops to <30mL/min during the course of the study, study medication should be stopped and bridging therapy may be considered. Study drug dabigatran etexilate can be re-started if CrCl recovers to ≥ 30 mL/min within seven days; otherwise it should be permanently discontinued for the duration of the trial and the patient followed until the trial completes. A patient should also be permanently discontinued from study drug, if CrCl drops to <30mL/min at two different occasions during the trial. See [Section 3.3.4.1](#).

Warfarin Treated Group:

Preoperative Phase:

Bridging therapy with a parenteral anticoagulant should be considered depending on the length of study drug interruption. Bridging therapy is at the discretion of the Investigator and can be performed according to local practice (see [Appendix 10.1](#) for guidance).

Post Procedural Period:

Anticoagulation can be started as soon as clinically feasible with i.v. (unfractionated) or s.c. LMWH and simultaneously with study warfarin until the INR is ≥ 2.0 . Parenteral bridging therapy should be stopped when target INR is achieved (see Appendix 10.1 for guidance).

Spinal Anaesthesia/Epidural Anaesthesia/Lumbar Puncture

Dabigatran and Warfarin Treated Group:

Procedures such as spinal anaesthesia may require complete haemostatic function. See [Table 4.2.1.3: 1](#) for recommendations on when to stop dabigatran before spinal/epidural anaesthesia. For patients randomised to Warfarin, INR measurements should be performed to ensure that coagulation is under control.

The risk of spinal or epidural haematoma may be increased in cases of traumatic or repeated puncture and by the prolonged use of epidural catheters. After removal of a catheter, resume treatment with study medication after complete haemostasis is achieved, but at minimum an interval of at least one hour should elapse for all patients. These patients require frequent observation for neurological signs and symptoms of spinal or epidural haematoma.

Proprietary confidential information.

© 2016 Boehringer Ingelheim International GmbH or one or more of its affiliated companies. All rights reserved.

This document may not - in full or in part - be passed on, reproduced, published or otherwise used without prior written permission.

4.2.1.4 Stroke

Patients with documented or suspected stroke should be managed according to usual clinical practice. It is anticipated that in most cases study drug will be withheld until a computed tomography (CT) or magnetic resonance (MR) imaging scan has been obtained.

Ischaemic stroke:

For ischaemic stroke, ASA and/or clopidogrel, or ASA/dipyridamole (the latter in lieu of clopidogrel) may be administered as indicated according to usual clinical practice. Anticoagulation with the study drug can be continued at the discretion of the local Investigator, in the absence of evidence of bleeding [[P13-06400](#)].

Fibrinolytics may be considered for ischaemic stroke, if a normal aPTT, ECT or TT test is obtained for patients receiving dabigatran etexilate, or if the INR is ≤ 1.7 in patients receiving warfarin.

Haemorrhagic stroke:

For haemorrhagic stroke or other intracranial bleeding, consultation with a coagulation expert and a neurosurgeon is recommended.

See [Section 4.2.1.1](#) and [Figure 4.2.1.1: 1](#) for details relating to how to manage bleeding on dabigatran etexilate or warfarin.

Reintroduction of study treatment following a stroke:

Dabigatran Etexilate Treated Group:

The decision about restarting dabigatran etexilate following a stroke is at the discretion of the Investigator. The following recommendations on when to restart dabigatran etexilate are provided for guidance only.

Table 4.2.1.4: 1 Recommendations on restarting dabigatran etexilate following a stroke [[P12-02400](#)]

Stroke Severity	Restart of Dabigatran etexilate
TIA	as soon as imaging has excluded a cerebral haemorrhage
Mild Stroke	3-5 days after stroke onset
Moderate Stroke	5-7 days after stroke onset
Severe Stroke	2 weeks after stroke onset

Proprietary confidential information.

© 2016 Boehringer Ingelheim International GmbH or one or more of its affiliated companies. All rights reserved.

This document may not - in full or in part - be passed on, reproduced, published or otherwise used without prior written permission.

Warfarin Treated Group:

The decision about restarting study warfarin following a stroke and its exact timing is at the discretion of the Investigator.

4.2.1.5 Acute Coronary Syndrome

In patients with documented or suspected ACS, study drug should be temporarily discontinued if other anticoagulants (e.g. UFH) are deemed necessary. ASA, clopidogrel and glycoprotein IIb/IIIa inhibitors may be administered according to usual clinical practice.

Dabigatran Etxilate Treated Group:

In patients receiving dabigatran etexilate, unfractionated or low-molecular-weight heparin should be withheld until at least 12 hours have passed since the last dose of dabigatran etexilate or the aPTT is less than 1.5 x ULN.

- If the aPTT is between 1.2 and 1.5 x ULN, UFH may be commenced with or without a loading dose at the discretion of the physician and LMWH may be commenced at the usual therapeutic dose (without an i.v. loading dose)
- If the aPTT is above 1.5 times the ULN, it should be repeated every four hours until it falls below this level, after which heparin or other anticoagulation can be commenced.

Warfarin Treated Group:

Unfractionated or low-molecular-weight heparin (or other anticoagulants) may be administered in warfarin treated patients according to usual clinical practice.

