4.2.2 Restrictions

4.2.2.1 Restrictions regarding concomitant treatment

Corticosteroids or NSAIDs may be used if clinically indicated according to current treatment guidelines but it is strongly recommended to avoid these if possible. It should be noted that the use of any of these agents with warfarin or dabigatran etexilate is likely to increase the risk of bleeding.

The following treatments should not be taken during the active treatment phase of the trial:

1. Treatment with ticlopidine or prasugrel
2. Fibrinolytic agents (see [Section 4.2.1.4](#) for exception)
3. GPIIb/IIIa antagonists (e.g. abciximab, tirofiban)
4. Treatment with systemic ketoconazole, itraconazole, posaconazole, cyclosporine, tacrolimus, dronedarone and rifampicin, phenytoin, carbamazepine or St. John's Wort
5. Dipyridamole, rivaroxaban, apixaban and edoxaban, or other oral anticoagulants (e.g. VKAs)
6. ASA - except where specified in the protocol for patients randomised to the warfarin arm or in both treatment arms after 12 months of treatment if clopidogrel or ticagrelor is switched to ASA ($\leq 100\text{mg q.d.}$) at Investigator discretion. The patients should be advised to not use additional ASA-containing over-the-counter medications.

The Investigator is alerted to the use of concomitant administration of moderate to strong P-gp inhibitors (e.g. such as amiodarone, verapamil, quinidine, nelfinavir, posaconazole, ritonavir, saquinavir and tipranavir+ritonavir or lopinavir+ritonavir) or P-gp inducers in this study due to a potential risk of higher or lower plasma levels of dabigatran and consequent exaggerated or reduced pharmacodynamic effect of dabigatran etexilate (notably bleeding risk). Concomitant use of such drugs is not prohibited in this study *per se* (except for treatment with ketoconazole, itraconazole, posaconazole, cyclosporine, tacrolimus, dronedarone, rifampicin, phenytoin, carbamazepine or St. John's Wort), but should be used with caution or, at Investigator discretion, switched to a suitable alternative.

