The concomitant use of dabigatran etexilate with the following treatments has not been studied and may increase the risk of bleeding: UFHs (except at doses necessary to maintain patency of central venous or arterial catheter) and heparin derivatives, low molecular weight heparins (LMWH), fondaparinux, desirudin, thrombolytic agents, GPIIb/IIIa receptor antagonists, ticlopidine, dextran, sulfapyrazone, rivaroxaban, apixaban, edoxaban, prasugrel, direct thrombin inhibitors, VKAs and the P-gp inhibitors itraconazole, tacrolimus, cyclosporine, ritonavir, tipranavir, nelfinavir and saquinavir.

Bleeding risk may be increased in patients concomitantly treated with selective serotonin re-uptake inhibitors ([U11-1642-01](#)) or selective serotonin norepinephrine re-uptake inhibitors ([U12-1072-01](#)).

Co-administration of oral anti-platelet (including ASA) and NSAID therapies increase the risk of bleeding ([U09-3249-02](#)). Specifically, with concomitant intake of antiplatelets or strong P-gp inhibitors in patients aged ≥ 75 years, the risk of major bleeding, including GI bleeding, increases.

If bleeding is clinically suspected, appropriate measures such as testing for occult blood in stool, or testing for a drop in haemoglobin is suggested ([U12-1072-01](#)). Investigators should assess the benefit-risk of the concomitant use of drugs that can promote bleeding, e.g., NSAIDs, corticosteroids and ASA, other anticoagulants and use them only when the benefits are thought to outweigh the risks.

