D2.1	Prohibited medication use	
The following treatments should not be taken during the active treatment period of the trial (at least one on-treatment use, unless otherwise stated):
 
 1. Treatment with ticlopidine or prasugrel 2. Fibrinolytic agents (see Section 4.2.1.4 of the protocol for exceptions) 3. GPIIb/IIIa antagonists (e.g. abciximab, tirofiban) 4. Treatment with systemic ketoconazole, itraconazole, posaconazole, cyclosporine, tacrolimus, dronedarone and rifampicin, phenytoin, carbamazepine or St. John's Wort (only applicable to patients randomised to dabigatran etexilate) 5a. Dipyridamole (although it is allowed for exceptional cases based on CTP Section, 4.2.1.4; for the PPS analyses all patients with on-treatment use will be excluded), 5b. Other oral anticoagulants (e.g. VKAs) 
Commercial NOACs (dabigatran, rivaroxaban, apixaban and edoxaban):
 
Warfarin Patients: At the end of the treatment, flag patients with more than 2 days of overlap of warfarin and commercial NOAC + flag any days of overlap during the treatment period (except for washout of previous treatment/titration at study start (see IPV C4))
 
Dabigatran patients: At the end of treatment, flag patients with more than 1 day of overlap of dabigatran and commercial NOAC + flag any days of overlap during the treatment period (except for washout of previous treatment/titration at study start (see IPV C4))
 
Commercial VKAs:
 
Dabigatran patients: At the end of treatment, flag patients with more than 5 days of overlap of dabigatran and commercial VKA +flag any days of overlap during the treatment period (except for washout of previous treatment/titration at study start (see IPV C4))
 
Warfarin patients: At the end of treatment, flag patients with more than 1 day of overlap of warfarin and commercial VKA. +flag any days of overlap during the treatment period (except for washout of previous treatment/titration at study start (see IPV C4))
 
 6. ASA in the first 12 months for all patients – except for in the first month for warfarin patients with a BMS or the first three months for warfarin patients with a DES (consecutive use of more than 14 days) 	PPS

Table 6.2: 1 (continued) Important protocol violations

Category/ Code	Description	Example/Comment	Excluded from
D2.2	Prohibited use of heparin	Any on-treatment use of heparin where no medical indication is given.	PPS

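### SAP violation code D2.1 item 3 counts GPIIb/IIIa inhibitor use that Protocol 4.2.1.5 permits in ACS as an important protocol violation and a PPS exclusion, because Protocol 4.2.2.1 item 3 lacks the exception pointer that item 2 carries

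*Protocol*

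**What the plan says.** Protocol 4.2.1.5 covers a patient with documented or suspected ACS while in the trial. It states that "ASA, clopidogrel and glycoprotein IIb/IIIa inhibitors may be administered according to usual clinical practice". Study drug is to be interrupted only if another anticoagulant is needed.

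Protocol 4.2.2.1 opens its list of barred drugs with "The following treatments should not be taken during the active treatment phase of the trial". Item 2 (fibrinolytics) points to Section 4.2.1.4 for an exception. Item 3 reads "GPIIb/IIIa antagonists (e.g. abciximab, tirofiban)" and has no pointer. Item 5 begins "Dipyridamole, rivaroxaban, apixaban and edoxaban, or other oral anticoagulants (e.g. VKAs)" and also has none, although Section 4.2.1.4 says that after ischaemic stroke "ASA/dipyridamole (the latter in lieu of clopidogrel) may be administered as indicated according to usual clinical practice".

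SAP Table 6.2:1, code D2.1, turns this list into an important protocol violation (IPV). One on-treatment use is enough unless an item says otherwise, and the consequence is exclusion from the PPS. Item 2 there keeps its exception: "Fibrinolytic agents (see Section 4.2.1.4 of the protocol for exceptions)". Item 3 repeats the GPIIb/IIIa entry with nothing added. Item 5a acknowledges that dipyridamole is sometimes permitted and excludes those patients from the PPS on purpose.

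**The concern.** The PPS is meant to hold treated patients who followed the protocol without an IPV (SAP 6.3). Under D2.1 item 3, a patient whose ACS was managed as Protocol 4.2.1.5 allows counts as not having followed it. The patient is tabulated among the PPS-excluding violators (SAP 7) and by default leaves the PPS analysis of the primary bleeding endpoint. The trigger is a clinical event after randomisation, not a departure by the site or the patient.

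At stake are the accuracy of the violation tables, the meaning of one sensitivity analysis, and the clarity of the instruction to sites.

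**Working it through.** The plan gives no figure for this point, so the check is a comparison of texts. All of them are current text, not entries in the amendment description.

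**1. Permission, prohibition and SAP treatment, by drug**

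| Drug | Permitted in an acute event | Barred in Protocol 4.2.2.1 | Exception pointer there | SAP D2.1 |
|---|---|---|---|---|
| Fibrinolytics | 4.2.1.4, ischaemic stroke | item 2 | yes, to 4.2.1.4 | item 2: exception kept |
| GPIIb/IIIa inhibitors | 4.2.1.5, ACS | item 3 | none | item 3: no exception, no acknowledgement |
| Dipyridamole | 4.2.1.4, ischaemic stroke | item 5 | none | item 5a: permission acknowledged, exclusion deliberate |

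**2. The other D2.1 items.** Item 1 (ticlopidine, prasugrel) has no adaptation, but the protocol permits those drugs nowhere. Item 4 is limited to dabigatran patients. Item 5b sets tolerated days of overlap at the end of treatment. Item 6 needs more than 14 consecutive days of ASA. Item 3 is the only entry that the protocol expressly permits in some setting and that has no exception, tolerance or acknowledgement.

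**3. Does interrupting study drug avoid the flag?** No. Under Protocol 4.2.1.5 a GPIIb/IIIa inhibitor alone does not require an interruption. If study drug is interrupted, SAP 6.1 still runs the on-treatment period from first to last intake and disregards gaps. Use during the gap is on-treatment use, and D2.1 needs only one.

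**4. Reach.** In SAP Table 6.3:1 the primary endpoint is the only outcome endpoint analysed on the PPS. The FAS is the main set, and neither FAS nor TS membership depends on D2.1. The PPS analysis may be omitted if fewer than 10% of the TS are excluded for all reasons together. If all 2,502 planned patients are treated, 0.10 × 2,502 = 250.2, so up to 250 exclusions would still allow it to be omitted.

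**5. Number of patients.** The documents give no rate of ACS on treatment and no rate of GPIIb/IIIa use, so neither a count nor a direction of bias can be derived.

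**The case against.** The best defence is that the specific rule governs the general one. Section 4.2.1.5 is the ACS rule. Section 4.2 also says that drugs needed for the patient's welfare "may be given at the discretion of the Investigator and with due consideration of the information provided below". Item 3 still has work to do outside ACS: the PCI paragraph of 4.2.1.6 names ASA, clopidogrel and ticagrelor, but not GPIIb/IIIa inhibitors. SAP item 5a shows that the sponsor reads the acute-event sections as exceptions even where 4.2.2.1 has no pointer. Removing such patients from a sensitivity analysis of bleeding is defensible too. Protocol 4.2.2.1 lists GPIIb/IIIa receptor antagonists under the warning "The concomitant use of dabigatran etexilate with the following treatments has not been studied and may increase the risk of bleeding". Finally, set membership is settled at the report planning or database lock meeting.

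Most of this stands, and it keeps the point small. A site can work with the protocol, so the documents do not support an inference that patients would be denied treatment. The defence does not repair the SAP: item 3, read literally, still flags permitted use, and a bleeding-risk reason would need stating, as item 5a does. Correction at a meeting is a weaker safeguard than a prespecified rule in an open-label trial.

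Three stronger readings are tempting but not supported:

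- **Parity with heparin.** D2.2 flags heparin only where no medical indication is given, so a reader might infer unequal treatment of similar drugs. But heparin is not on the prohibited list, and the protocol repeatedly allows parenteral bridging. The two drugs differ in protocol status, and the SAP follows that status.
- **Exclusion only from the start of use.** C3, D3.1 and D3.2 work that way, but they concern assigned or mandatory medication not taken as required. C1, C4, D2.2 and G1 exclude the whole patient, as D2.1 does. Partial exclusion would be a preference, not a correction.
- **An analysis error for dipyridamole.** Item 5a already handles it openly. Only the protocol pointer is missing.

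**Conclusion.** The point holds as a minor error of wording with a limited effect on analysis. Followed as written, D2.1 item 3 labels protocol-permitted GPIIb/IIIa use in ACS an important violation and removes the patient from the PPS. This rests on reading item 3 literally and on the SAP 6.1 definition of the on-treatment period.

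A reader might infer that the non-inferiority conclusion is at risk. The documents do not support that, because the main analysis uses the FAS. Nor can a share of lost follow-up be given: the timing of ACS is unknown, and the 18-month average in Protocol 3.2 is trial participation, not on-treatment time.

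**What to change.** - **Protocol 4.2.2.1 item 3:** add *see Section 4.2.1.5 for exception*, mirroring item 2.
- **SAP Table 6.2:1, D2.1 item 3:** add the same exception, so that GPIIb/IIIa use for ACS is not counted as an IPV. If the sponsor prefers to keep such patients out of the PPS because of bleeding risk, state that in the item, in the manner of item 5a.
- **Optional:** add a pointer to Section 4.2.1.4 for dipyridamole in Protocol 4.2.2.1 item 5.

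The cost is one or two cross-references in the protocol and one edit in the SAP table. Data collection, sample size, and the FAS and TS analyses are unaffected.
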